8.3.5 Pharmacokinetic Analysis

The population PK model developed in melanoma patients will be used to obtain individual vemurafenib PK parameters from the sparse sampling collected in newly enrolled patients. Summary statistics (such as mean, median and standard deviation) will be used as appropriate for the vemurafenib plasma concentrations and PK parameters.

The relationship between appropriate clinical and pharmacodynamic endpoints and the plasma concentrations of vemurafenib will be explored, as appropriate.

8.3.6 Exploratory Analyses

The correlation between plasma and tissue BRAF V600 mutation status as well as the concordance of the Roche CoDx cobas 4800 BRAF V600 Test or other standard methodologies may be explored. The relationship between appropriate clinical endpoints and the mutation status (including, but not limited to, allelic frequencies of the BRAF V600 mutation and its dynamic changes from pre-dose to on-treatment) in tissue and/or plasma will be explored. Mutation status in tissue and/or plasma will also be correlated to demographics, medical history and clinical parameters.

8.3.7 Other Analyses

Demographics and medical history will be summarized for each cohort.

8.4 SAMPLE SIZE ESTIMATION

The sample size estimation is based on the method of Lin and Shih ([70](#)) and corresponding SAS program.

There will be up to 170 patients enrolled in this study for the Stage I/II analysis (see [Table 15](#)). Recruitment into any cohort/indication can be expanded up to a total of 70 patients if a response rate has been demonstrated in Stage II of that cohort as per stopping rules defined in the protocol or a clear clinical benefit for patients is observed. This will be decided by the Sponsor in discussion with study Steering Committee. The maximum number of patients in this study is therefore 490 (7 cohorts up to 70 patients each).

There will be 7 cohorts with patients with different indications. There will be two sub- cohorts with patients with colorectal cancer, one treated only with vemurafenib while other treated with vemurafenib and cetuximab.

Cohorts (except Cohort 3b and Cohort 7) will have a minimum of 13 and a maximum of 19 patients (depending on results in Stage I).

If there are enough patients enrolled in individual tumour type, Cohort 7 will have 13 or 19 patients and Lin and Shin's method of Stage I and Stage II design will be applied. If there are not enough patients in individual tumour type, data for cohort 7 will be only listed.

Cohort 3b will have a dose escalation phase based on a classical 3+3 design and will enrol a maximum of 18 patients. Cohort of patients with MTD will be expanded to 7 patients as per rule of Stage I design. Then a further 6 or 12 patients will be enrolled to a maximum of 13 or 19 patients will be enrolled depending on the results for stage I (see [Table 16](#)). The maximum number of patients for this cohort might be up to 37 patients.

A proportion of 15% is chosen for a low response, based on [Section 8.3.1.1](#) in the protocol and on our present knowledge.

However, if the number of responders is 2, 3, or 4 out of 7 patients in Stage I, then the study medication is possibly efficacious for that cohort and further data at stage II will be collected based on the "low desirable response at Stage II" Sample Size estimation, i.e., an additional 12 patients will be enrolled in order to have a total of 19 patients for that cohort. Stage I will be stopped if the number of responders is less than the pre-specified number in the [Table 15](#) (e.g. if there is none or only one responder out of first seven patients). However if a clear clinical benefit has been observed for patients in the cohort, e.g. majority of patients recorded SD at Week 8 and no CR or PR is recorded, then enrolment into Stage II will be allowed for this cohort after discussion with the Sponsor and study Steering Committee.

If there are 5 or more responders out of 7, then further data will be collected based on "high desirable response at Stage II" Sample Size estimation, i.e., an additional 6 patients will be enrolled in order to have a total of 13 patients for that cohort.

Assuming RRs as specified in the prior hypothesis testing, a power of 80% for high desirable response and 70% for low desirable response and two-sided alpha of 0.1, the number of patients required in each cohort is presented in [Table 16](#).

Table 15:
Sample Size for Each Cohort – Stage I/II

	Dose Finding ^a	Sample size following Stage I analysis	
		Low desirable response	High desirable response
NSCLC		19	13
Ovarian cancer		19	13
Colorectal cancer (Cohort 3a vemurafenib only)		19	13
Colorectal cancer (Cohort 3b vemurafenib and cetuximab)	3+3 Design up to 18	19	13
Cholangiocarcinoma/cancer of biliary tract		19	13
Breast Cancer		19	13
Multiple Myeloma		19	13
Other tumours ^b		19	13
Total number for Stage I/II	up to 170 patients ^c		

- a. Cohort 3b Part 1 only
- b. The n's presented are for each individual tumour type, with enough patients available to follow the 2 stage study design
- c. The total number of patients may exceed the original estimate of 170 patients if any cohort is expanded (see [Table 16](#)).

Details regarding Stage I and number of responders are presented in [Table 16](#).

Table 16:
Sample Size for Each Cohort (except Cohort 6) and Stage I/II

	Stage (Two-Stage Design)		Total Number of Patients in Each Cohort	Two-Sided Alpha Level / Power
	Stage I	Stage II ^b		
All Cohorts				
Low response at the end of Stage I				
Number of patients	7	19	19	10% / 70%
Number of responders ^a	≥ 2 and ≤ 4	≥ 5		
High response at the end of Stage I				
Number of patients	7	13	13	10% / 80%
Number of responders ^a	≥ 5	≥ 6		

The sample size was estimated using the method of Lin and Shih's paper (Biometrics. 2004;60:482-490) and corresponding SAS program.

Number of patients needed to respond in order to continue into Stage II or have a positive result at the end of trial.

- a. This columns display a maximum number of patients required for each cohort and number of responders that should be present at end of Stage II in order to declare efficacious treatment.

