8.3.1.1 Hypothesis Testing

The adaptive two-stage design allows the original estimation of the Stage II RR to be reassessed, based on information at Stage I, in the event that it was too optimistic or too sceptical to be the true RR.

For example, for patients in each cohort, we assume that an RR of 15% would be a very low RR and vemurafenib would be "under-performing" for this cohort. An RR of 45% would be a high desirable RR, whereas an RR of 35% would be a low desirable RR, for Stage II.

The hypotheses for all cohorts for Stage I are:

$$H_0: \pi_{N1} < \pi_0 \text{ where } \pi_0 = 15\%$$

$$H_1: \pi_{N1} \geq \pi_0 \text{ where } \pi_0 = 15\%$$

If H_0 is rejected (and H_1 is accepted at Stage I), further patients will be enrolled based on the number of responders in Stage I and their data will be collected in the second stage.

The hypotheses for all cohorts at the end of Stage II for a low desirable response, π_{1L} , are:

- i) H_1 is accepted at Stage I and
- ii) $H_0: \pi_N \leq \pi_{1L}$ where $\pi_{1L} = 35\%$

$$H_1: \pi_N > \pi_{1L} \text{ where } \pi_{1L} = 35\%$$

The N notifies the total number of patients for each cohort.

The hypotheses for all cohorts at the end of Stage II for a high desirable response, π_{1H} , are:

- i) H_1 is accepted at Stage I and
- ii) $H_0: \pi_N \leq \pi_{1H}$ where $\pi_{1H} = 45\%$

$$H_1: \pi_N > \pi_{1H} \text{ where } \pi_{1H} = 45\%$$

Cohort 3b

For this cohort, first, the recommended dose for Stage I/II part should be established based on 3+3 classical design. Then the second part will include a stage I and II parts similar to what is planned for the other cohorts and same statistical hypotheses at Stage I and Stage II will be applied.

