8.3.2 Efficacy Data Analysis

The primary efficacy endpoint is RR at Week 8 in each cohort, as assessed by the Investigator using RECIST, v1.1 or IMWG response criteria.

This is an early phase II study and cohorts are independent, hence there will be no adjustment for multiplicity.

Number and percentage of responders with corresponding Clopper-Pearson 95% confidence intervals will be provided for each cohort. The clinical benefit rate, BOR and RR at the end of Stage II will be analysed in a similar way to RR at Week 8. Estimates for the survivor function for the time-to-event variables, such as time to progression (TTP), PFS, OS, duration of response, and time to response, will be obtained by using the Kaplan-Meier (KM) approach together with associated 95% CI.

Due to the small sample size in Cohort 7 (patients with other solid tumours), only descriptive statistics will be applied. If there are at least 5 patients with the same tumour type, number (percentage) of patients will be summarized in the frequency table and listed for RR at Week 8, clinical benefit rate and BOR. If there are fewer patients, only listings will be provided. For response criteria for patients with prostate cancer, ECD and/or LCH enrolled in this cohort, see [Appendix 9](#) and [Appendix 10](#), respectively.

In case a cohort/indication is expanded up to 70 patients, the primary analysis for efficacy will occur once all patients have been followed up for 9 months after last patient had been enrolled in that cohort, or the patient develops progressive disease, withdraws consent, or is lost to follow-up, whichever occurs first.

For all patients in Cohort 1, the CT scans during the patient's last therapy prior to this study, as well as CT scans made during this study, will be collected and reviewed retrospectively by an IRC. Scans from the prior therapy will be used to establish pITT, and this may be examined in relation to the TTP achieved from study treatment. During the study, the investigator-assessed response rate will remain as the primary efficacy endpoint and the IRC assessment will be a supportive secondary endpoint. The concordance tables between Investigator and IRC assessment will be produced. The IRC assessment of response rates will focus on Week 8, Week 16 and BOR. For other cohorts, collection of scans are described in the study assessment sections. Analyses will be performed as described above for Cohort 1.

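### The 10% alpha is labelled two-sided, but the Table 16 responder counts spend 10% in the upper tail alone, so the stated 10%/70% is true only as a one-sided alpha

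*Protocol*

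**What the plan says.** Section 8.4 states "a power of 80% for high desirable response and 70% for low desirable response and two-sided alpha of 0.1". The synopsis has the same sentence. Table 16, and its synopsis copy Table 2, give 10% / 70% for the 19-patient branch and 10% / 80% for the 13-patient branch under the header "Two-Sided Alpha Level / Power".

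The reference rates are in Sections 8.4 and 8.3.1.1: "A proportion of 15% is chosen for a low response", "an RR of 35% would be a low desirable RR, for Stage II" and "An RR of 45% would be a high desirable RR".

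The count rule per cohort is:
- 0 or 1 responder in 7: stop.
- 2 to 4 in 7: continue to 19; success at 5 or more.
- 5 or more in 7: continue to 13; success at 6 or more.

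Section 8.3.1.2 counts a cohort as a success when responders reach or exceed the tabulated number, so the rule looks upward only. It also allows success through a confirmed best overall response above 15%, and allows a cohort that misses the Stage I count to continue at discretion on stable disease.

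For reporting, Section 8.3.2 says: "Number and percentage of responders with corresponding Clopper-Pearson 95% confidence intervals will be provided for each cohort".

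**The concern.** A two-sided alpha of 0.10 is conventionally read as 5% in each tail. A rule that can only succeed upward should then carry a false-positive probability of about 5% at the undesirable rate. If it carries 10%, the label misdescribes the design.

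The label matters because the protocol makes no multiplicity adjustment across cohorts, so the per-cohort alpha is the only error control it states. Meeting the count also supports declaring the treatment efficacious and can open expansion to 70 patients. A reader who takes the label in its usual sense would believe the count rule is twice as strict as it is.

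**Working it through.** **Inputs.** Rates of 15%, 35% and 45% (Sections 8.4 and 8.3.1.1); Stage I size 7, totals 19 and 13, and the success counts (Section 8.4, Table 16).

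**Choice of null.** Section 8.3.1.1 writes the Stage II null hypotheses at 35% and 45%, but the error is evaluated here at 15%. This is the only reading that returns a figure near 10%: the same rule succeeds about 70% of the time at 35%.

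**Formula.** Let b(x; 7, p) be the binomial probability of x responders in Stage I. Then

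P(success | p) = Σ over x = 2..4 of b(x; 7, p) · P(Bin(12, p) ≥ 5 − x) + Σ over x = 5..7 of b(x; 7, p) · P(Bin(6, p) ≥ 6 − x).

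**At p = 0.15:**

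| Stage I responders | b(x; 7, 0.15) | P(reach final count) | Product |
|---|---|---|---|
| 2 | 0.2097 | P(Bin(12) ≥ 3) = 0.2642 | 0.0554 |
| 3 | 0.0617 | P(Bin(12) ≥ 2) = 0.5565 | 0.0343 |
| 4 | 0.0109 | P(Bin(12) ≥ 1) = 0.8578 | 0.0093 |
| 5 | 0.0012 | P(Bin(6) ≥ 1) = 0.6229 | 0.0007 |
| 6 or 7 | 0.0001 | 1 | 0.0001 |

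The 19-patient branch contributes 0.0990 and the 13-patient branch 0.0008, for a total of **0.0998**.

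**Reproducing the stated figures.**
- At 35%: 0.6532 + 0.0521 = **0.7053**, against the stated 70%.
- At 45%: 0.7330 + 0.1497 = **0.8827**, above the stated 80%.

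So 10%/70% is reproduced, with the whole 10% in the upper tail.

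**If 5% in the upper tail were meant.** At least 5/19 is ruled out whatever the 13-patient threshold, because that branch alone spends 0.0990. The lowest workable count is at least 6/19. With at least 6/13 unchanged:
- Error at 15%: 0.0417 + 0.0008 = 0.0425.
- Power at 35%: 0.5605 + 0.0521 = 0.6126.
- Power at 45%: 0.7016 + 0.1497 = 0.8513.

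Lowering the 13-patient count to 5 raises power at 35% only to 0.6161. At N = 19, 5% in the upper tail and 70% power at 35% cannot both hold.

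**Scope of the 9.98%.** It covers the Table 16 counts alone. Suppose the alternative criterion is read as an observed rate above 15% and confirmed best overall response is assumed equal to the response rate. Since 0.15 × 19 = 2.85 and 0.15 × 13 = 1.95, 3/19 or 2/13 suffices. At 15% the probability of success is then 0.2097 × 0.8578 + 0.0617 + 0.0109 + 0.0012 = 0.2537, or 0.2536 without rounding the terms: about 25%.

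**Reported interval (95% Clopper-Pearson).**

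| Responders | Interval | Includes 15%? |
|---|---|---|
| 5/19 | 9.1% to 51.2% | Yes |
| 6/19 | 12.6% to 56.6% | Yes |
| 7/19 | 16.3% to 61.6% | No |
| 6/13 | 19.2% to 74.9% | No |

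**The case against.** The strongest defence is that only a word is wrong. The rule has no lower rejection region, so its total probability of a false declaration at 15% is the printed 10%. The protocol nowhere writes 5%. The stated 70% power shows that 10% in the upper tail was intended, and the at-least-6/19 design is one nobody proposed. This stands in full as to consequence: no count, sample size or decision needs to change. It does not rescue the label, because an upward-only rule with 10% in that tail is a one-sided 10% rule.

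Three stronger readings are tempting, and the document does not support them.

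- **That the 95% interval contradicts the decision.** The protocol provides the interval for reporting and never makes it a decision criterion. It includes 15% at 5/19 and 6/19 but not at 6/13. It would still include 15% at 6/19, the count that respects 5%, so the label does not cause the mismatch. A fixed-sample 95% interval beside a two-stage 10% test will often differ.
- **That 9.98% is the true error of an efficacy declaration.** Section 8.3.1.2 offers the best-overall-response route as an alternative and allows continuation on stable disease. Both can only raise the error.
- **That an extra two-stage confidence limit is needed to match the decision.** At 5/19 a one-sided 90% limit falls at 15.01% or 14.99%, depending on how outcomes at 13 and 19 patients are ordered. Such a limit does not reliably settle agreement at the threshold.

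**Conclusion.** The concern holds as a wrong statement of a design property. The Table 16 counts have an exact upper-tail error of 9.98% at 15%, with power of 70.5% at 35% and 88.3% at 45%. The label in Section 8.4, the synopsis and both table headers should say one-sided. Read conventionally, the present label implies half that error, and the protocol's own counts and power exclude that reading.

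This rests on 15% as the null, independent binomial responses, and strict use of the Table 16 counts. The 25% for the alternative criterion rests further on confirmed best overall response equalling the response rate; it would be lower if confirmation removes responders. Discretionary continuation is not sized because the protocol gives no rate for it.

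**What to change.** - In Section 8.4 and the sample size text of the synopsis, replace "two-sided alpha of 0.1" with: one-sided alpha of 0.10. Change the header of Tables 2 and 16 to match.
- Add one sentence saying that this error rate applies to the tabulated responder counts alone. It does not apply to the alternative criterion of confirmed best overall response above 15%, or to cohorts continued on stable disease.
- Keep the 95% Clopper-Pearson interval and describe it as descriptive. Note that at 5/19 and 6/19 it includes 15% although the cohort meets the success count. No further interval is required.

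If the sponsor did intend 5% in the upper tail, relabelling is not enough: the 19-patient threshold must rise, and the cohort must be re-sized to keep 70% power at 35%.

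The cost is wording only, with no patients, thresholds or outputs added. The one drawback is that the stated error looks less favourable.

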8.4.1 Sample Size Estimation for Expansion of Cohorts following Promising Stage II Results

Recruitment into any cohort/indication can be expanded up to a total of 70 patients if a response rate has been demonstrated in Stage II of that cohort as per stopping rules defined in the protocol or a clear clinical benefit for patients is observed. This will be decided by the Sponsor in discussion with study Steering Committee.

Assuming a preferable BOR of 40% in the cohort with promising Stage II results and aiming at a distance from the estimated proportion to the CI limits of 12%, a total of 70 patients would need to be enrolled. The observed BOR of 40% could then be estimated to be within 28% and 52%, with a probability of 95% (Clopper-Pearson exact confidence intervals).

Estimation of the sample size was calculated by SAS (Version 9.2) and nQuery (Version 6). Details are presented in the [Table 17](#).

**Table 17:
Estimation of Sample Size**

Sample Size	BOR	95% Clopper Pearson Exact Confidence Intervals
70 patients	36% (25 patients)	25% – 48%
	40% (28 patients)	28% – 52%
	46% (32 patients)	34% – 58%
	50% (35 patients)	38% – 62%

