3. Cohort Expansion

There will be no formal statistical hypothesis tested as part of the expansion cohort analysis. The analysis of the expanded cohort will allow estimation of RR and other efficacy parameters (please refer to secondary efficacy parameters in [Section 8.1.2](#)) with increased precision and more insight concerning the safety profile.

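### Expanded-cohort response rates pool the Stage I/II patients whose responses triggered expansion, so on the response route the estimate is biased upward: about 2 to 4 points at a true 15%, under 1 point at 40%

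*Protocol*

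**What the plan says.** Section 8.4.1 sets the route to expansion: "Recruitment into any cohort/indication can be expanded up to a total of 70 patients if a response rate has been demonstrated in Stage II", read against the protocol's stopping rules, "or a clear clinical benefit for patients is observed". The decision rests with the sponsor in discussion with the Steering Committee. The size is justified by precision at an assumed BOR of 40%: "aiming at a distance from the estimated proportion to the CI limits of 12%, a total of 70 patients would need to be enrolled". The conclusion drawn is that "The observed BOR of 40% could then be estimated to be within 28% and 52%, with a probability of 95" per cent, and Table 17 gives four such intervals at 70 patients.

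The stopping rules in Section 8.3.1.2 and Table 16 ask for at least 2 responders among 7 at Stage I, then at least 5 of 19 (after 2 to 4 at Stage I) or at least 6 of 13 (after 5 or more). Stage II also accepts, as an alternative to the count, a confirmed BOR above 15%.

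On analysis, Section 8.3.2 states: "Number and percentage of responders with corresponding Clopper-Pearson 95% confidence intervals will be provided for each cohort". Section 8.3.1.2, item 3, makes the expansion an estimation exercise without a test: "The analysis of the expanded cohort will allow estimation of RR and other efficacy parameters". Sections 8.3.1 and 8.3.2 call the analysis of the whole expanded cohort, after 9 months of follow-up, its primary efficacy analysis.

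**The concern.** A Clopper-Pearson interval at 70 describes 70 patients taken as one sample of fixed size. A cohort that expands on response is not such a sample. Its first 13 or 19 patients are there because they showed enough responses, and those responses are counted again in the final rate. The later patients dilute the selection but do not remove it.

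The effect is largest where the drug is weak and the cohort passed by luck. Those are the cohorts that extra patients should expose, in a trial that aims to pick tumour types for further development. Because the protocol presents the expansion as estimation with better precision, bias and coverage are the properties that matter.

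**Working it through.** **The plan's own figures.** Clopper-Pearson 95% limits at 70 patients:

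- 25/70: 24.6% to 48.1%
- 28/70: 28.5% to 52.4%
- 32/70: 33.7% to 58.1%
- 35/70: 37.8% to 62.2%

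All four rows of Table 17 reproduce to within rounding. Around 40% the distances to the limits are 11.5 and 12.4 points, against the aim of 12.

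**Inputs for the check.**

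- Stage I: 7 patients, at least 2 responders (Section 8.4, Table 16).
- Stage II total N = 19 after 2 to 4 responders, N = 13 after 5 or more.
- Strict rule: at least 5/19 or 6/13 (Table 16).
- Full rule: that count, or BOR above 15%. Since 0.15 × 19 = 2.85 and 0.15 × 13 = 1.95, this means at least 3/19 or 2/13.
- Final size 70, so 70 − 19 = 51 or 70 − 13 = 57 patients join after the decision.
- Reference rate 15%, from Section 8.3.1.1: "we assume that an RR of 15% would be a very low RR".
- Assumption: one and the same binary response drives the decision and the final rate.

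**Formulas.** With b the binomial probability, x1 and x2 the responders among the first 7 and the next N − 7, and k the responders among 70:

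f(k) = Σ b(x1; 7, p) · b(x2; N − 7, p) · b(k − x1 − x2; 70 − N, p), summed over the (x1, x2) that pass.

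P(expand) = Σ f(k). Mean pooled rate = Σ k f(k) / (70 · P(expand)). Lower-limit error = sum of f(k) over all k whose lower limit exceeds p, divided by P(expand). At p = 15% the first such k is 18: the lower limit is 14.8% for 17/70 and 16.0% for 18/70.

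**Results at a true 15%.**

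| | Strict rule | Full rule | Unselected 70 |
|---|---|---|---|
| P(expand) | 9.98% | 25.4% | – |
| Mean pooled rate | 18.95% | 17.15% | 15% |
| Lower limit above 15%, given expansion | 6.41% | 3.22% | 1.35% |
| Ratio to nominal 2.5% | 2.56 | 1.29 | 0.54 |
| Two-sided coverage, given expansion | 93.6% | 96.7% | – |

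The pooled bias is 18.95 − 15 = 3.95 points (strict) or 17.15 − 15 = 2.15 points (full).

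**Results at a true 40%, the protocol's own scenario.** Mean pooled rate 40.7% (strict) or 40.5% (full); lower-limit error 2.4% or 2.3%; coverage 96.7% or 96.5%. An interval for 28/70 that conditions on having passed is 27.2% to 52.0% (strict) or 27.7% to 52.1% (full), close to the printed 28% to 52%. For 18/70 the conditional lower limit is 13.1% or 14.5%, against 16.0% unadjusted.

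**Patients enrolled after the decision.** Their lower-limit error at 15% is 1.6% (51 patients) or 1.9% (57 patients), with no selection bias. The price is width. For 20/51 = 39.2% the interval is 25.8% to 53.9%, so the distances are 39.2 − 25.8 = 13.4 and 53.9 − 39.2 = 14.7 points.

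**The case against.** A reader might infer that the lower limit errs 2.6 times as often as the protocol states. The documents do not support that as the headline figure. It needs the Table 16 counts to be the only route to expansion, whereas Section 8.3.1.2 also accepts BOR above 15% and Section 8.4.1 also allows clinical benefit. Under the full response rule the ratio is 1.3. If cohorts with no responders among 7 may also enter Stage II on clinical benefit, it falls to about 1.1. The protocol also states two-sided 95% and makes no separate claim about the lower tail.

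Nor does the overall chance of a misleading result rise. At a true 15%, the probability that a cohort expands and then has a lower limit above 15% is 0.0998 × 0.0641 = 0.64% (strict) or 0.2536 × 0.0322 = 0.82% (full), both below the 1.35% for an unselected 70. The excess exists only among cohorts that were expanded. No section judges an expanded cohort by whether its lower limit clears 15%.

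It is equally tempting to call the printed 28% to 52% wrong, or to want conclusions based on the post-decision patients alone. The first is a correct fixed-sample calculation. The second is a trade-off: under the full rule the pooled estimate has the smaller root-mean-square error at 15% (4.6 against 5.0 points) and at 40% (5.8 against 6.8), with only a marginal reversal near 10% (4.3 against 4.2). Under the strict rule pooling is better from 20% up. The post-decision interval also misses the 12-point aim.

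Finally, a supplementary table is something an analysis plan could add, and that plan is not at hand. All of this stands and limits the size of the point. It does not remove the bias: the protocol itself fixes the pooled total, the interval method and the 95%, and its statistical sections do not mention the selection.

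**Conclusion.** The point holds as a modest one. On the response route the pooled expanded-cohort rate is biased upward and its interval takes no account of how the first 13 or 19 patients came to be included. The size depends on which Stage II criterion triggers expansion: at a true 15%, about 2 to 4 points of bias and a lower-limit error of 1.3 to 2.6 times nominal among expanded cohorts. At the 40% used for planning the effect is negligible.

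All figures assume identical binary responses at the decision and at the end. The protocol decides Stage I on unconfirmed responses while Table 17 concerns confirmed BOR, and it gives no correlation between them. Imperfect correlation, like expansion on clinical benefit, would make the bias and the error smaller.

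**What to change.** In Sections 8.3.1.2 (item 3), 8.3.2 and 8.4.1:

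- Keep the pooled 70 as the main estimate.
- For every expanded cohort, report beside it the RR and BOR with Clopper-Pearson 95% intervals in the patients enrolled after the Stage II decision (51 or 57), as a supportive estimate free of this selection.
- State that the Table 17 intervals do not allow for the Stage I/II selection.

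The cost is one extra table per expanded cohort and a few lines of text, with no extra patients. The supportive interval is wider: about 26% to 54% for 20/51, against the printed 28% to 52% for 28/70.
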